#### CONFIDENTIAL JUVÉDERM® VOLUMA® with Lidocaine injectable gel

examinations or laboratory testing was planned, this assessment may be performed as an unscheduled or follow-up visit.

If travel restrictions or other changes in local regulations in light of a pandemic or natural disaster prevent the participant from in-clinic visits, participant visits may be conducted via phone, video conference, or remotely.

# 8.2.1. Clinical Safety Laboratory Assessments

Hematology and blood chemistry tests will be performed as described in Appendix 10.2.

At screening, the TI will assess the clinical significance of any values outside the reference ranges provided by the laboratory, and participants with abnormalities judged to be clinically significant will be excluded from the study.

The TI must review the laboratory report and document this review and record any clinically relevant changes occurring during the study in the AE section of the eCRF. The laboratory reports must be filed with the source documents. Clinically significant abnormal laboratory findings are those that are not associated with the underlying disease, unless judged by the TI to be more severe than expected for the participant's condition.

All laboratory tests with values considered clinically significantly abnormal during participation in the study are to be repeated until the values return to normal or baseline or are no longer considered clinically significant by the investigator.

- If such values do not return to normal/baseline within a period of time judged reasonable by the investigator, the etiology is to be identified and the sponsor notified.
- All protocol-required laboratory assessments, as defined in Appendix 10.2, must be conducted in accordance with the SoA (Section 1.3).
- If laboratory values from non-protocol specified laboratory assessments performed at the institution's local laboratory require a change in participant management or are considered clinically significant by the investigator (eg, SAE or AE or dose modification), then the results must be recorded as an SAE or AE in the eCRF.
- Urine or blood pregnancy tests will be used at the study site at screening, before each study treatment, and at study exit for female participants of childbearing potential.
- If a participant who underwent at least 1 treatment withdraws from the study before the Month 6 visit, he/she must be followed up for hematology test, clinical chemistry, and routine urinalysis at study exit for safety.

# 8.3. Adverse Events and Serious Adverse Events

AEs will be monitored throughout the study beginning with signing of the ICF. At each postbaseline visit, the TI will begin querying for AEs by asking each participant a general, nondirected question such as "Have you had any changes to your condition since your last visit?" Previous AEs and changes in therapy/concomitant medications are to be updated. Directed questioning and examination will then be done as appropriate. All reportable AEs and clinically significant abnormal laboratory findings will be documented on the appropriate eCRF.

The definitions of an AE/ADE or SAE/SADE and their severity can be found in Appendix 10.7.

AEs/ADEs will be reported by the participant (or, when appropriate, by a caregiver, surrogate, or the participant's legally authorized representative).

The PI/TI and any qualified designees are responsible for detecting, documenting, and recording events that meet the definition of an AE/ADE or SAE/SADE and remain responsible for following up AEs/ADEs that are serious, considered related to the study intervention or study procedures, or that caused the participant to discontinue the study (see Section 7).

Pandemic infections should be captured as AEs. If the event meets the criteria for an SAE, then follow the SAE reporting directions per the protocol.

#### 8.3.1. Time Period and Frequency for Collecting AE and SAE Information

All SAEs/SADEs from the signing of the ICF until the last follow-up visit will be collected at the timepoints specified in the SoA (Section 1.3), and as observed or reported spontaneously by study participants.

All AEs/ADEs from the signing of the ICF until the last follow-up visit will be collected at the timepoints specified in the SoA (Section 1.3), and as observed or reported spontaneously by study participants.

Medical occurrences that begin before the start of study intervention, but after obtaining informed consent will be recorded in the AE section of the eCRF and will be considered pretreatment AEs.

All SAEs/SADEs will be recorded and reported to the sponsor or designee within 24 hours, as indicated in Appendix 10.7. The PI/TI will submit any updated SAE data to the sponsor within 24 hours of it being available.

PIs/TIs are not obligated to actively seek AE/ADE or SAE/SADE information after conclusion of the study participation. However, if the PI/TI learns of any SAE/SADE, including a death, at any time after a participant has been discharged from the study, and he/she considers the event to be reasonably related to the study intervention or study participation, the PI/TI must promptly notify the sponsor.

# 8.3.2. Method of Detecting AEs and SAEs

The method of recording, evaluating, and assessing causality of AEs/ADEs and SAEs/SADEs and the procedures for completing and transmitting SAE/SADE reports are provided in Appendix 10.7.

Care will be taken not to introduce bias when detecting AEs/ADEs and/or SAEs/SADEs. Open-ended and nonleading verbal questioning of the participant is the preferred method to inquire about AE/ADE/SAE/SADE occurrences.

#### 8.3.3. Follow-up of AEs and SAEs

After the initial AE/ADE/SAE/SADE report, the TI is required to proactively follow each participant at subsequent visits/contacts. All AEs/ADEs/SAEs/SADEs will be followed until resolution, stabilization, the event is otherwise explained, or the participant is lost to follow-up (as defined in Section 7.3).

The PI/TI is obligated to perform or arrange for the conduct of supplemental measurements and/or evaluations as medically indicated or as requested by the sponsor medical safety physician to elucidate the nature and/or causality of the AE/ADE or SAE/SADE as fully as possible. This may include additional laboratory tests or investigations, histopathological examinations, or consultation with other health care professionals.

If a participant dies during participation in the study or during a recognized follow-up period, the PI/TI will provide the sponsor medical safety physician with a copy of any postmortem findings including histopathology.

New or updated information will be recorded in the originally completed eCRF.

The PI/TI will submit any updated SAE/SADE data to the sponsor within 24 hours of receipt of the information.

#### 8.3.4. Regulatory Reporting Requirements for SAEs

- Prompt notification by the PI/TI to the sponsor of an SAE/SADE is essential so that legal obligations and ethical responsibilities towards the safety of participants and the safety of a study intervention under clinical investigation are met.
- The sponsor has a legal responsibility to notify both the local regulatory authority and other regulatory agencies about the safety of a study intervention under clinical investigation. The sponsor will comply with country-specific regulatory requirements relating to safety reporting to the regulatory authority, IECs, and investigators.
- A PI who receives an investigator safety report describing an SAE/SADE or other specific safety information (eg, summary or listing of SAEs/SADEs) from the sponsor will review and then file it along with the IB and will notify the IEC, if appropriate according to local requirements.

#### 8.3.5. Pregnancy

- Details of all pregnancies in female participants will be collected after the start of study intervention and until the last follow-up visit.
- If a pregnancy is reported, the PI/TI is to inform the sponsor within 24 hours of learning of the pregnancy.
- The PI/TI shall (1) instruct the participant to notify her physician of the presence of the investigational device and (2) follow the pregnancy to term or termination. Best practices are to be followed in order to ensure the welfare of the participant and the fetus. The sponsor medical safety physician will contact the PI/TI to obtain information about the pregnancy outcome. The participant will continue to be followed, and the pregnancy will be documented as a protocol deviation.
- The pregnancy outcome of a spontaneous or elective abortion, stillbirth or congenital anomaly is considered a SAE and must be reported to AbbVie within 24 hours after the site becomes aware of the event.

#### 8.3.6. Medical Device Deficiencies

Medical devices are being provided for use in this study as the study intervention. In order to fulfill regulatory reporting obligations worldwide, the PI/TI is responsible for the detection and documentation of events meeting the definition of device deficiency that occur during the study with such devices.

The definition of a medical device deficiency can be found in Appendix 10.7.

NOTE: Device deficiencies fulfilling the definition of an AE/SAE will also follow the processes outlined in Section 8.3.3 and Appendix 10.7 of the protocol.

- Medical device events or malfunctions of the device that result in an incident will be detected, documented, and reported during all periods of the study in which the medical device is used.
- If the PI/TI learns of any device deficiency at any time after a participant has been discharged from the study, and such an event is considered reasonably related to a medical device provided for the study, the PI/TI will promptly notify the sponsor.

The method of documenting medical device deficiencies is provided in Appendix 10.7.

#### 8.3.6.2. Follow-up of Medical Device Deficiencies

- Follow-up applies to all participants, including those who discontinue study intervention or the study.
- The investigator is responsible for ensuring that follow-up includes any supplemental investigations as indicated to elucidate the nature and/or causality of the deficiency.
- The device deficiency will be reported to the sponsor by email. If email is unavailable, then fax will be used.
- The same individual will be the contact for the receipt of device deficiency reports and SAEs.

#### 8.3.6.3. Prompt Reporting of Device Deficiencies to Sponsor

- Device deficiencies that are potentially related to SAEs will be reported to the sponsor within 24 hours after the PI/TI determines that the event meets the protocol definition of a medical device deficiency.
- The medical device deficiency will be reported to the sponsor by email. If email is unavailable, then fax will be used.
- The sponsor will be the contact for the receipt of device deficiency reports.

#### 8.3.6.4. Regulatory Reporting Requirements for Device Deficiencies

- The PI/TI will promptly report all device deficiencies occurring with any medical device provided for use in the study in order for the sponsor to fulfill the legal responsibility to notify appropriate regulatory authorities and other entities about certain safety information relating to medical devices being used in clinical studies.
- The PI, or responsible person according to local requirements (eg, the head of the medical institution), will comply with the applicable local regulatory requirements relating to the reporting of device deficiencies to the IEC.

# 8.4. Treatment of Overdose

Overdose is not applicable for this study.

## 8.5. Pharmacokinetics

Pharmacokinetic parameters are not evaluated in this study.

#### 8.6. Pharmacodynamics

Pharmacodynamic parameters are not evaluated in this study.

### 8.7. Genetics

Genetics are not evaluated in this study.

# 8.8. Biomarkers

Biomarkers are not evaluated in this study.

#### 8.9. Immunogenicity Assessments

Immunogenicity is not evaluated in this study.

#### 8.10. Health Economics

Health economics parameters are not evaluated in this study.

# 9. Statistical Considerations

A separate SAP will be prepared to provide specifications for all analyses. The plan will be finalized and approved prior to clinical database lock. The database will be locked and analyzed at the end of study (all data collected through the end of the study).

In general, descriptive statistics will be presented. Categorical variables will be summarized with response frequencies and percentages. Continuous variables will be summarized by descriptive statistics for the number of participants, mean, median, standard deviation, Q1, Q3, minimum, and maximum. Where appropriate, 2-sided 95% CIs for mean or proportion will be provided as part of the summary.

Every attempt will be made to collect complete data and limit the occurrence of missing data. No imputation of missing data is planned, except for the primary effectiveness analyses as described in Section 9.4.2.2. Deviations from the analyses planned in the SAP will be documented in the clinical study report.

Statistical analysis activities will be conducted by the Coordinating Investigator or by a third party delegated by the Coordinating Investigator.

# 9.1. Statistical Hypotheses

The null and alternative hypotheses are:

Ho: 
$$P_v = P_c$$
  
Ha:  $P_v \neq P_c$ 

where  $P_v$  and  $P_c$  denote the responder rates for the treatment group at Month 6 after last control-period treatment, and control group at Month 6 after randomization, respectively (responder is defined as a participant with at least 1-grade improvement on the ATHS in both temples based on the EI's live assessment of temple hollowing). The null hypothesis for effectiveness is that the responder rate at Month 6 is the same for the treatment and control groups. The alternative hypothesis is that the ATHS responder rate for the treatment group is different from the control group at Month 6.

# 9.2. Sample Size Determination

The primary effectiveness measure is the change from baseline on the 5-point ATHS at Month 6. The change can range from -4 to +2. The primary effectiveness variable is the ATHS responder status, which is determined by an improvement of 1 grade or more (ie, a change score of -4 to -1) in both temples.

Under a 2:1 randomization ratio, a total of 90 participants in the treatment group and 45 participants in the control group at the primary timepoint will provide at least 90% power to detect a difference of 30% in the responder rates between the groups. This calculation is based on a 2-sided Fisher's exact test at the 5% level, using responder rates of 65% and 35% for both temples simultaneously for participants in the treatment and control groups, respectively. The assumption of a 65% treatment responder rate is a conservative estimate based on the observed responder rate in previous filler studies for other facial areas. Also, while a 30% difference from control is greater than a minimally important difference, a 35% responder rate is a reasonable upper limit of expectation for the control group, based on validation results of the ATHS and control group responder rates observed in previous filler studies. Furthermore, assuming a dropout rate of 20% after randomization through the Month 6 visit, 168 randomized participants are needed, with 112 participants in the treatment group and 56 participants in the control group (2:1 ratio).

If the underlying true responder rate is 65%, 90 participants in the treatment group results in a binomial likelihood of 86.5% to observe a responder rate of at least 60%.

With up to 9 investigational sites planned, it is recommended that no site randomize more than twice the proportional share of 1 more site =  $2 \times [168/(n+1)]$ . The recommended minimum is 8 participants per site, which will guarantee that each treatment group has at least 2 participants at each site (allowing for mixed randomization blocks of 3 and 6 that incorporate the 2:1 randomization ratio).

The commercial software PASS (2008, Version 8.0.13) was used for the power calculation. The sample size calculation used an inequality test for 2 proportions to demonstrate that the treatment group is superior to the control group.

Due to local guidelines to prevent and mitigate the effects of a pandemic or natural disaster, it is understood that some participants may not be able to complete all site visits as indicated per protocol. If more than 20% of the randomized participants fail to complete the primary timepoint ATHS assessment in-clinic, additional participants will be enrolled.

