### **Overall Design**

- Multicenter, randomized, controlled, parallel-design study in participants with minimal, moderate, or severe temple hollowing (Grade 2, 3, or 4 on the ATHS)
- Single-blind: EIs are blinded; treating investigators (TIs) and participants are not blinded
- VOLUMA with Lidocaine injected with 27 G 1/2" or 25 G 1" needles to the supraperiosteal plane in the temple area (up to 3 mL per temple for initial and touch-up treatments combined) for the treatment group and delayed treatment for the control group

**Disclosure Statement:** This is a parallel-design treatment study with 2 arms that is blinded to EIs.

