# 4. Study Design

# 4.1. Overall Design

This is a prospective, multicenter, evaluator-blinded, randomized, parallel-group, no-treatment controlled study to evaluate the safety and effectiveness of VOLUMA with Lidocaine HA injectable gel to correct temple hollowing.

The study will involve up to 9 investigational sites. The study population is represented by Chinese adults who are seeking correction of temple hollowing and who meet the study criteria according to the study design.

Participants will be randomized in a 2:1 ratio of treatment group to control group.

Participants will stay in the study for up to 14 months depending on their randomization group. For the treatment group, each participant will be in the study for up to 14 months: up to 1 month for screening, up to 30 days of treatment, and up to 12 months of follow-up after last treatment. For the control group, each participant will be in the study for 7 months (up to 1 month for screening and 6 months for follow-up) and then may exit or opt to receive study intervention. Control participants who opt to receive study intervention will be in the study for an additional 7 months (up to 30 days for treatment and 6 months of follow-up), for a total of 14 months.

The study will compare the treatment to no treatment, with the primary timepoint set at Month 6 (for treatment group, 6 months after last treatment; for control group, 6 months after randomization). Each site will have a PI who is responsible for the overall conduct of the study at that site and may also serve as the TI. The TI performs all study treatments and safety assessments, and the blinded EI evaluates ATHS and GAIS.

The study design is single-blind where the EIs and image analysis technicians will remain blinded to each participant's assigned study intervention throughout the course of the study. The PIs/TIs, study coordinators, and participants will not be blinded to treatment, and they will secure the randomization and other records (eg, records of study treatments and prior study assessments) from potential discovery by the blinded EIs. The TIs will not discuss the randomized treatment assignments with or in the presence of the EIs. Additional precautions to keep blinding are outlined in Section 6.3.

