# 5.2. Exclusion Criteria

Participants are excluded from the study if any of the following criteria apply:

1.	Medical Conditions
1.01	The participant cannot achieve at least a 1-grade improvement for each temple from the EI's baseline score on the ATHS given the allowed injection volume, in the opinion of the TI
1.02	Has temple hollowing due to trauma, congenital malformations, or lipodystrophy, either congenital or acquired
1.02	Additional examples include: congenital myotonic dystrophy, HIV-associated lipodystrophy, or acquired generalized lipodystrophy
1.03	Has experienced trauma to the temple area within 6 months before enrollment or has residual deficiencies, deformities, or scarring
1.04	Atrophic skin in the temple area that might not be suitable for injection, in the opinion of the TI
1.05	Temporal arteritis or history of temporal arteritis
1.06	Temporomandibular joint dysfunction or any other jaw issues
1.07	Recurrent temporal headaches such as temporal tendonitis migraine

1 00	
1.08	Tendency to develop hypertrophic scarring
1.09	History of anaphylaxis or allergy to lidocaine (or any amide based anesthetics) HA products or
1.10	Streptococcal protein
1.11	Current cutaneous or mucosal inflammatory or infectious processes (eg, acne, herpes), abscess, an unhealed wound, or a cancerous or precancerous lesion, above the subnasale
2.	Prior/Concomitant Therapy
2.01	Prior facial reconstructive surgeries, face-lift, or brow lift as well as surgeries on the temple area (eg, biopsy)
2.02	Fat injection or permanent facial implants (eg, polymethylmethacrylate, silicone, polytetrafluoroethylene) in the temple area
2.03	Fat injection or permanent facial implants (eg, polymethylmethacrylate, silicone, polytetrafluoroethylene) in facial areas other than the temples within 12 months before enrollment
2.04	Semipermanent soft-tissue filler treatment (eg, calcium hydroxylapatite, poly-L-lactic acid) in the temple or mid-face within 36 months before enrollment
2.05	Temporary dermal filler injections above the subnasale within 12 months before enrollment
2.06	Temporary dermal filler injections in the nasolabial fold or below the subnasale within 3 months prior to enrollment
2.07	Botulinum toxin treatment above the subnasale or at masseter muscle within 6 months before enrollment
	Mesotherapy or cosmetic facial procedures above the subnasale within 6 months before enrollment

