#### 6.3. Measures to Minimize Bias: Randomization and Blinding

Prior to initiation of study intervention, each consented participant will be assigned a participant number that will be recorded on the appropriate eCRF. At the time of randomization (ie, at the Randomization/Initial Treatment visit), eligible participants will be randomly assigned at a 2:1 ratio to treatment group or control group. For all treatments, the right side will be treated first. Randomization will be within each study site. All participants will be centrally randomized using an IWRS. Before the study is initiated, the log-in information and directions for the IWRS will be provided to each site.

Study intervention will be injected at the study visits summarized in the SoA (Section 1.3). Instructions for preparing and administering the study intervention are provided in the IDFU and IB.

If participants are withdrawn, they will not be replaced.

The EIs and image analysis technicians will remain blinded to each participant's assigned study intervention throughout the course of the study. The PIs/TIs, study coordinators, and participants will not be blinded to treatment, and they will secure the randomization and other records (eg, records of study interventions and prior study assessments) from potential discovery by the

blinded EI. The TIs will not discuss the randomized treatment assignments with or in the presence of the EIs.

In order to maintain the blind, the EI will not be present during any treatment visits and will not have access to any unblinding information (such as treatment eCRFs or device accountability logs). In addition, participants will be instructed not to discuss whether they have received treatment with the EI. Image analysis technicians will only have access to image files that will not contain any unblinding information (such as randomization status or visit name).

In the event of a Quality Assurance audit, the auditor(s) will be allowed access to unblinded study intervention records at the sites to verify that randomization/dispensing has been done accurately.

The EI must remain blinded throughout the study. If a participant requires immediate medical attention by an unblinded physician, this must be provided by the TI whenever possible. In the event that no unblinded physician is available to provide such treatment, the investigational site or sponsor staff may break the blind so that the EI can provide treatment.

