#### 2.4 Sample Size Determination

The primary effectiveness measure is the change from baseline on the 5-point ATHS at Month 6. The primary effectiveness variable is the ATHS responder status, which is determined by an improvement of 1 grade or more (i.e., a change score of -4 to -1) in both temples.

Under a 2:1 randomization ratio, a total of 90 participants in the treatment group and 45 participants in the control group at the primary timepoint will provide at least 90% power to detect a difference of 30% in the responder rates between the groups. This calculation is based on a 2-sided Fisher's exact test at the 5% level, using responder rates

of 65% and 35% for both temples simultaneously for participants in the treatment and control groups, respectively. The assumption of a 65% treatment responder rate is a conservative estimate based on the observed responder rate in previous filler studies for other facial areas. Also, while a 30% difference from control is greater than a minimally important difference, a 35% responder rate is a reasonable upper limit of expectation for the control group, based on validation results of the ATHS and control group responder rates observed in previous filler studies. Furthermore, assuming a dropout rate of 20% after randomization through the Month 6 visit, 168 randomized participants are needed, with 112 participants in the treatment group and 56 participants in the control group (2:1 ratio).

With 7 investigational sites planned, it is recommended that no site randomize more than approximately 42 participants (i.e., twice the proportional share of 1 more site =  $2 \times [168/8]$ ). The recommended minimum is 8 participants per site, which will guarantee that each treatment group has at least 2 participants at each site (allowing for mixed randomization blocks of 3 and 6 that incorporate the 2:1 randomization ratio).

The commercial software PASS (2008, Version 8.0.13) was used for the power calculation. The sample size calculation used an inequality test for 2 proportions to demonstrate that the treatment group is superior to the control group.

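### The protocol and SAP print the within-site block sizes (3 and 6), so unblinded site staff can be certain of about 9% of upcoming allocations, against almost none if the sizes were withheld

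*Protocol*

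**What the plan says.** The block sizes appear in a parenthesis in Protocol 9.2 (Sample Size Determination): "allowing for mixed randomization blocks of 3 and 6 that incorporate the 2:1 randomization ratio". SAP 2.4 repeats them: "allowing for mixed randomization blocks of 3 and 6". They are there to support a recommended minimum of 8 participants per site.

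Protocol 6.3 sets the level and route of allocation: "Randomization will be within each study site. All participants will be centrally randomized using an IWRS". Randomization takes place at the Day 1 visit.

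On blinding, the synopsis says "Single-blind: EIs are blinded; treating investigators (TIs) and participants are not blinded", and Protocol 4.1 says "The PIs/TIs, study coordinators, and participants will not be blinded to treatment". Site staff therefore know the full allocation history of their own site.

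The TI confirms eligibility (Table 1-1, footnote c). Several criteria rest on the TI's opinion. Exclusion 1.01 removes a participant who, in that opinion, "cannot achieve at least a 1-grade improvement for each temple from the EI's baseline score" given the permitted volume; 1.04 and 5.03 are also discretionary. Neither document says that the block sizes are kept from sites.

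**The concern.** Varying the block size is meant to hide where a block ends. Printing the two sizes in a document that every site holds gives part of that protection away. An unblinded TI who knows the sizes and the site's history can sometimes deduce the next allocation before deciding whether, or when, to bring a candidate to the randomization visit. A central IWRS conceals the list, but it cannot conceal what follows from the list's own rules and past output.

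What is at stake is selection. Exclusion 1.01 forecasts a gain of at least one grade in each temple, and the primary endpoint is a gain of at least one grade in both temples. Favouring likely responders when a treated slot is expected would enrich the treated arm. Blinding the evaluator protects the scoring, not the composition of the arms, and the planned Fisher comparison has no covariate adjustment.

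**Working it through.** **Inputs.** Block sizes 3 and 6 at 2:1, so 2 treated and 1 control, or 4 treated and 2 control (Protocol 9.2, SAP 2.4). Blocking within site (Protocol 6.3). Mean site size 168/9 = 18.7 with the protocol's 9 sites, or 168/7 = 24 with the SAP's 7. The mixing probability of the two sizes is not given; 50:50 is assumed, with a range of 75:25 to 25:75.

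**The plan's own figure.** The worst case for controls is a block of 3 (1 control) followed by a block of 6 that opens with its 4 treated: 3 + 4 = 7 participants with 1 control. The eighth must be a control. So 8 per site does guarantee 2 per arm, and the stated minimum is exact.

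**How certainty arises.** Suppose a site opens control, control. A block of 3 holds only one control, so this is a block of 6 with its controls used up, and the next four are treated for certain. The chance is 0.5 × (2/6 × 1/5) = 1/30. If a site opens with four treated, the next two are control for certain; the chance is 0.5 × (4/6 × 3/5 × 2/4 × 1/3) = 1/30. An observer who thinks that a block of 9 or 12 is possible can be certain in neither case.

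**General calculation.** Let (t, c) be the treated and control places left in the current block, with weight w(t, c). A new block starts at (2, 1) or (4, 2) with probability 0.5 each. Then

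P(next is control) = Σ w(t, c) × c/(t + c).

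After each allocation the weights are multiplied by t/(t + c) or c/(t + c) and rescaled. The comparison observer sees the same sequences but holds a flat prior over 3, 6, 9 and 12 (an assumption). Results by simulation, site of 19 unless stated:

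| Quantity | Sizes known | Sizes withheld |
|---|---|---|
| Certain allocations | 9% | about 0% |
| of which control | 1.8% | 0% |
| Callable at 90% or better | 31% | 2% |
| of which control | 1.8% | 0% |
| Callable at 80% or better, treated (site of 18) | 36% | 35% |
| Callable at 80% or better, control (site of 18) | 4% | 0% |
| Best guess correct | 75% | 75% |
| Control call correct | 79% | 79% |
| Controls correctly flagged | 33% | 33% |

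Always guessing treated is right 66.7% of the time.

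**Scale and sensitivity.** Over the whole trial, 9% × 168 ≈ 15 certain allocations, of which 1.8% × 168 ≈ 3 are controls. Across mixes of 75:25 to 25:75, certain calls run from 5% to 13% (site of 18), and calls at 90% or better from 34% down to 23% (site of 19). For sites of 18 to 42 at 50:50, certain calls stay at 9–10%.

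**What larger blocks would do.** With sizes 6, 9 and 12 in equal shares, and even with the sizes known, a site of 18 gives about 2% certain calls and a hit rate of about 71%. The site guarantee changes, because a block of 12 can open with 8 treated: 8 participants may include no control, and 8 + 2 = 10 are needed for two. If size 3 is kept alongside 12, a block of 3 followed by those 8 treated gives 11 participants with one control, so 12 are needed.

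**The case against.** The strongest reply is that disclosure causes little of the predictability. That stands for the broad measures: overall hit rate, accuracy of a control call and share of controls flagged are the same with the sizes withheld. The contrast of 31% with 2% also depends on the 90% threshold; at 80% the treated calls barely differ. What disclosure adds is certainty, plus the few high-confidence control calls, which are otherwise absent.

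The second reply is that the route to bias is narrow. The blinded evaluator grades both entry and endpoint. Screening procedures must precede randomization (Table 1-2, footnote c), and evaluations must be completed and reviewed with failure reasons logged (Protocol 8). Screen failures may not be rescreened (Protocol 5.4), so a rejected candidate cannot be saved for a later slot. Baseline ATHS and FACE-Q are tabulated by arm (SAP 7.1). Criterion 1.01 concerns response to injection, so steering poor candidates into an uninjected control arm has no evident way to lower its responder rate; only enrichment of the treated arm would matter. All of this stands. It narrows the route without closing it, since the TI can still act until Day 1 and defer within the 30-day screening window.

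A reader might infer that most allocations are foreseeable because the sizes were printed, or that the trial is open-label. Neither is supported: the 75% hit rate is not caused by disclosure, and the trial is evaluator-blinded with an unblinded TI and participants.

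**Conclusion.** The point holds as a modest, avoidable weakness in allocation concealment. Printing the sizes raises certain calls from about 0% to about 9% of allocations (5–13% across the mixes tried) and calls at 90% or better from about 2% to about 31%, nearly all of them treated, which is already the likelier arm under 2:1. These figures assume a 50:50 block mix, an observer who tracks the whole site history, and a flat prior over 3, 6, 9 and 12 for the comparison.

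The remaining predictability belongs to small within-site blocks with visible allocations and would survive deletion of the sentence. A reader might go on to infer that the responder-rate difference is biased. The documents do not support that: they give no evidence that anyone acted on a prediction, and guessability cannot be converted into an effect on the planned 30-point difference without further assumptions.

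**What to change.** 1. Delete the block sizes from Protocol 9.2 and SAP 2.4. State only that randomization is 2:1 and blocked within site, with the sizes held in a restricted randomization specification not available to sites. Align the Study Tabular Summary (Protocol 10.6), which lists no stratification factor. The cost is a sentence or two in each document.
2. Because the sizes are already in circulation, allocate anyone still to be randomized from a list with different, undisclosed sizes. This includes the additional participants that Protocol 9.2 allows if more than 20% miss the in-clinic primary assessment. The documents do not say whether enrolment was complete by the June 2023 SAP; if it was, this step applies only to such additions. The cost is a regenerated list.
3. If larger blocks are used, restate the site minimum: 10 for sizes 6, 9 and 12, or 12 if size 3 is kept with 12. Word the restated minimum so that it does not reveal the new sizes.
4. Optionally, lock the TI's eligibility decision in the IWRS before allocation is requested. This gives an audit trail; it does not prevent prediction and largely repeats the existing requirement to complete and review screening first.
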